#### **Assessment of Causality**

- The Investigator will assess the relationship between study intervention and each AE/SAE occurrence:
  - Unrelated: Not reasonably related to the study intervention. AE could not medically (pharmacologically/clinically) be attributed to the study intervention. A reasonable alternative explanation will be available.
  - Related: Reasonably related to the study intervention. AE could medically (pharmacologically/clinically) be attributed to the study intervention.
- A "reasonable possibility" of a relationship conveys that there are facts, evidence, and/or arguments to suggest a causal relationship, rather than a relationship cannot be ruled out.
- The Investigator will use clinical judgment to determine the relationship.
- Alternative causes, such as underlying disease(s), concomitant therapy, and other risk factors, as well as the temporal relationship of the event to study intervention administration will be considered and investigated.
- The Investigator will also consult the IB and/or Product Information, for marketed products, in his/her assessment.
- For each AE/SAE, the Investigator will document in the medical notes that he/she has reviewed the AE/SAE and assessed causality.
- There may be situations when an SAE has occurred, and the Investigator has minimal information to include in the initial report to the Sponsor or its designee. To meet the reporting timeline, the causality assessment is not required for the initial report.
- The Investigator may change his/her causality assessment after considering follow-up information and send an SAE follow-up report with the updated causality assessment.
- The causality assessment is one of the criteria used when determining regulatory reporting requirements.

#### **Follow-up of AEs and SAEs**

- The Investigator will perform or arrange for the conduct of supplemental measurements and/or evaluations, as medically indicated or as requested by the Sponsor/designee to elucidate the nature and/or causality of the AE or SAE, as fully as possible. This may include additional laboratory tests or investigations, histopathological examinations, or consultation with other health care professionals.
- If a participant dies during participation in the study or during a recognized follow-up period, the Investigator will provide the Sponsor/designee with a copy of any post-mortem findings including histopathology.
- New or updated information will be recorded in the originally completed CRF.
- The Investigator will submit any updated SAE data to the Sponsor/designee within 24 hours of receipt of the information.

## Reporting of SAEs

SAE Reporting by an Electronic Data Collection Tool

• The primary mechanism for reporting an SAE in multicenter studies to the Sponsor or its designee will be the electronic data collection tool.

• If the electronic system is unavailable, then the site will use the paper SAE form, specified below, to report the event within 24 hours.

• The site will enter into the electronic system the SAE data within 24 hours after becoming aware of the event. It is expected that the Investigator/Subinvestigator signs off this data in the system and any relevant associated data (e.g., additional laboratory tests, medical records, diagnostic reports, histopathological examinations, or consultation with other health care professionals) will be entered as soon as it becomes available.

• After the study is completed at a site, the electronic data collection tool will be taken off-line to prevent the entry of new data or changes to existing data.

• If a site receives a report of a new SAE from a study participant or receives updated data on a previously reported SAE after the electronic data collection tool has been taken off-line, then the site can report this information on a paper SAE form or to the Sponsor's safety department.

• By exception, an SAE (or follow-up information) may be reported by telephone. The site will complete the electronic SAE data entry immediately thereafter.

SAE Reporting by a Paper Form


• SAE reporting on a paper report form may be used in single center studies in addition to the standard electronic CRF and as a back-up method for an EDC system failure. The form includes completion instructions for the Investigator, names, addresses, and telephone and fax numbers. All information from the paper form will be transcribed into the electronic form as soon as the system becomes available.

• Facsimile transmission (fax to mail) of the paper form or any follow-up information is the preferred method for transmission and will be done within 24 hours to the Sponsor or its designee.

• In rare circumstances and in the absence of facsimile equipment, notification by telephone is acceptable with a copy of the form sent by overnight mail or courier service.

• Initial notification via telephone does not replace the need for the Investigator to complete and sign the form within 24 hours after becoming aware of the event.

• Additional documents (e.g., laboratory reports, autopsy report, hospital discharge letter) and relevant pages from the CRF may be required in addition (e.g., medical history, concomitant medication). The data provided will be consistent with the information in the CRF.

## Reporting of AESIs

• For a nonserious AESI, the site will complete the specific AESI report form and notify the Sponsor immediately (within 24 hours), using the same process for reporting SAEs, as specified above.

• For a serious AESI, the site will complete an SAE report form, using the SAE reporting process, specified above.

---

## Reporting of Pregnancies

• Pregnancy will be reported whether related to the study intervention using the applicable paper form.

• The applicable form will be used to report if an abnormal outcome of the pregnancy occurs and the child/fetus sustains an event.

• Facsimile transmission (fax to mail) of the paper form or any follow-up information is the preferred method for transmission and will be done within 24 hours to the Sponsor or its designee.

--

## Appendix 5    Liver Safety: Suggested Actions and Follow-up Assessments

The Investigator will consider discontinuation of study intervention for abnormal liver function when a participant meets one of the conditions outlined in the algorithm or if the Investigator believes that it is in best interest of the participant.

All confirmed events of ALT or AST  $\geq 5 \times$  ULN triggers stopping criteria.

All confirmed events of ALT or AST  $\geq 3 \times$  ULN and total bilirubin  $> 2 \times$  ULN triggers stopping criteria.

All AEs involving the liver or the gall bladder will be reported as AESI according to the risk profile of evobrutinib.

## Appendix 6    Clinical Laboratory Tests

The protocol-required clinical laboratory assessments are in the following table:

All study-required laboratory assessments will be performed by a central laboratory.

Laboratory Assessment	Parameter	Notes
Biochemistry	Albumin	
	Alanine Aminotransferase	
	Alkaline Phosphatase	
	Amylase	
	Aspartate Aminotransferase	
	Bicarbonate	
	Bilirubin	
	C-reactive protein	
	Calcium	
	Chloride	
	Creatinine	
	Cystatin C	
	Glomerular Filtration Rate, Estimated (by CKD-Epi)	
	Gamma Glutamyl Transferase	
	Glucose	
	Lactate dehydrogenase	
	Magnesium	
	Lipase	
	Potassium	
	Sodium	
	Protein	
	Urate	
Coagulation	Prothrombin Intl. Normalized Ratio	
Hematology	Hematocrit	
	Hemoglobin	
	Leukocytes with Differential:	
	Neutrophils (absolute/%)	
	Lymphocytes (absolute/%)	
	Monocytes (absolute/%)	
	Eosinophils (absolute/%)	
	Basophils (absolute/%)	

**Evobrutinib (M2951)    Relative Bioavailability of Evobrutinib Tablet Batches**  
**MS200527\_0131**

Laboratory Assessment	Parameter	Notes
	Ery. Mean corpuscular hemoglobin (MCH)	
	Ery. Mean corpuscular volume (MCV)	
	Platelets	
	Erythrocytes	
Hormonal	Follicle stimulating hormone	For postmenopausal women at Screening only
	Thyroid stimulating hormone	
Routine Urinalysis	Specific gravity, pH, glucose, protein, blood, ketones, bilirubin, urobilinogen, nitrite, leukocytes by dipstick	
	Microscopic examination (if blood or protein is abnormal).	In case of a positive result for hemoglobin, leukocyte esterase, protein or nitrite, a flow cytometry count and classification will be performed.
Pregnancy	Serum human chorionic gonadotropin pregnancy test, urine pregnancy test	Conducted at timepoints listed in the Schedule of Assessments
Alcohol and Drug Screen	Urine drug screen to include: 3,4-methylenedioxymethamphetamine (ecstasy), amphetamine, methamphetamine, barbiturate, cocaine, opiate, cannabinoids, benzodiazepine, methadone, phencyclidine, oxycodone, tricyclic antidepressants, cotinine Ethanol breath test	Screening and Day -1 only
Serology	HIV antibody, Hepatitis B Virus Surface Antigen, Hepatitis C Virus antibody, SARS-CoV-2 Antigen, SARS-CoV-2 RNA, and QuantiFERON® test	Screening only (except SARS-CoV-2 tests, also Day -1)

## Appendix 7 Protocol Amendment History

The information for the current amendment is on the title page.

3 Modification History

Unique Identifier for Version	Date of IAP Version	Author	Changes from the Previous Version
Final 1.0	06-FEB-2023	PPD	Initial Version

4 Purpose of the Integrated Analysis Plan

The purpose of this IAP is to document technical and detailed specifications for the final analysis of data collected for protocol MS200527_0131. Results of the analyses described in this IAP will be included in the CSR. Additionally, the planned analyses identified in this IAP may be included in regulatory submissions or future manuscripts. Any post-hoc, or unplanned analyses performed to provide results for inclusion in the CSR but not identified in this prospective IAP will be clearly identified in the CSR.

The IAP is based upon Section 9 (Statistical considerations) of the study protocol and protocol amendments and is prepared in compliance with ICH E9. It describes analyses planned in the protocol and protocol amendments.

The wording used in this IAP is chosen to best match the respective wording in the study protocol template, the CSR template, CDISC requirements and special requirements for table layouts. Therefore, the following approach is used:

Generally, the term 'participant' will be used instead of 'subject' or 'patient'. However, in tables and listings the term 'subject' will be used to match CDISC requirements, except for in-text tables where 'participant' will be used to match the CSR and protocol templates. Similarly, the term 'study intervention' will be used in this document instead of 'treatment' to match protocol and CSR templates, however, tables and listings will use 'treatment' for brevity reasons. Exceptions from this rule are commonly used terms like "on-treatment", "treatment-emergent", "treatment policy", "subject-years", "by-subject", or names of eCRF pages like "Treatment Termination" page.

5 Objectives and Endpoints

Objectives	Endpoints
Primary	
To compare the single-dose PK of different manufacturing batches of evobrutinib TF2 formulation relative to a reference batch under fasted conditions in healthy participants	AUC _{0-∞} and C _{max}
Secondary	

Objectives	Endpoints
To assess the safety and tolerability of evobrutinib administered as a single oral dose of different manufacturing batches of TF2 formulation under fasted conditions in healthy participants	Nature, occurrence, and severity of treatment-emergent adverse events (TEAEs) Absolute values and changes in safety laboratory tests Single 12-lead ECGs evaluated by Investigator (morphology and time intervals). Listing of the ECG description if classified as "abnormal". Vital signs assessed from time of first dose to end of study participation
To further characterize the PK of different manufacturing batches of evobrutinib TF2 formulation	Additional PK parameters, e.g. $AUC_{0-\text{last}}$, t_{max} , $t_{1/2}$, CL/F, V_z/F , F_{rel}

6 Overview of Planned Analyses

The final, planned analyses identified in the CSP and in this IAP will be performed after the last participant has completed the last visit and after all data queries resolved as well as the database locked.

A data review meeting will be held prior to database lock for the final analysis. In addition, no database can be locked until this IAP has been approved.

7 Changes to the Planned Analyses in the Clinical Study Protocol

There are no changes to the planned analyses in the clinical study protocol.

8 Analysis Sets and Subgroups

8.1 Definition of Analysis Sets

Analysis Set	Description
Screening (SCR)	All participants, who provided informed consent, regardless of the participant's enrollment and study intervention status in the study.
Safety (SAF)	All participants, who were administered any dose of any study intervention. Analyses will consider participants as treated.
Pharmacokinetic (PK)	The PK Analysis Set is a subset of the Safety Analysis Set and will consist of all participants who receive at least one dose of active IMP and provide at least one measurable postdose concentration. A measurement below lower limit of quantification is considered a valid measurement. Participants will be analyzed according to the actual treatment they received in each period. All PK analyses will be based on the PK Analysis Set.

PK=pharmacokinetic; SAF=safety; SCR=Screening.

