16.1.3 Statistical Analysis of PK Parameter Data

Analysis of Primary Endpoints

A linear mixed model with BATCH, PERIOD, and SEQUENCE as fixed effects and SUBJECT within SEQUENCE as a random effect will be applied to log-transformed primary endpoints C_{max} and $AUC_{0-\infty}$ based on the PK analysis set. Differences between batches (treatment A will be used as 'reference') on the log scale for each comparison will be estimated for the parameters together with their 90% CIs. Point estimates and CIs will be back transformed to the original scale by exponentiation for presentation. Ratio of geometric LSMEAN with 90% CI and geometric LSMEAN with 95 % CI will be presented.

Analysis of Secondary Endpoints

Summary statistics of PK parameters will be provided by study intervention.

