16.1.4 General Specifications for PK Concentration and PK Parameter Data

Predose samples that occur before the first drug administration will be assigned a time of 0 hours, as if the sample had been taken simultaneously with the study intervention administration.

Predose or trough samples which have been taken after the subsequent dosing will be reported as a protocol deviation. The resulting concentrations will be included in concentration listings but excluded from descriptive statistics of concentrations and from PK parameter estimation.

Values BLQ will be taken as zero for summary statistics of PK concentration data, PK parameter estimation (e.g., AUC) and for graphical presentations.

Missing concentrations (e.g., no sample, insufficient sample volume for analysis, no result or result not valid) will be reported generally as "N.R.". A participant who withdraws prior to the last planned observation will be included in the analyses up to the time of discontinuation if still included in the PK analysis set.

If samples are collected outside of the PK sampling time windows defined in the CSP in Section 8.4, these will be included in the PK parameter estimation (NCA) but will be excluded from the concentration summary and mean/median concentration plots.

PK concentrations which are erroneous due to a sampling processing or analytical error (as documented in the bioanalytical report) may be excluded from the PK analysis if agreed by the Sponsor. In this case the rationale for exclusion will be provided in the CSR. Any other PK concentrations that appear implausible to the Clinical Pharmacologist/Clinical PK/PD Scientist will not be excluded from the analysis. Any implausible data will be documented in the CSR.

If important protocol deviations occurred likely to affect the PK profile of participants as specified in Section 10.2.1, the impacted concentrations and PK parameters will be excluded from summary statistics and further statistical evaluation.

Any PK concentrations or PK parameters excluded from summary statistics will be included in participants listings and flagged; a reason for exclusion will be detailed in the CSR (e.g., a footnote or a table of exclusions). Any flags will be included in the study specific CDISC data sets.

PK concentrations and PK parameters excluded from summary statistics will not be included in mean/median figures. Mean plots will only contain values where $n > 2$.

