16.1.5.1 Estimation of Pharmacokinetic Parameters in Plasma

PK parameters will be calculated using the actual elapsed time since dosing. If the actual sampling time is missing, calculations may be performed using the scheduled time. Details (e.g., number of samples, participants affected) will be described in the CSR. If actual dosing time is missing, scheduled time might be used for NCA after performance of adequate plausibility checks and agreement with the sponsor. Decision and rational should be included in the CSR. Otherwise, there will be no further imputation of missing data.

The following plasma PK parameters will be calculated, when appropriate, for evobrutinib on Day 1 for each period:

Symbol	Definition
$AUC_{0-\infty}$	The AUC from time zero (= dosing time) up to infinity with extrapolation of the terminal phase.
$AUC_{0-t_{last}}$	The AUC from time zero (= dosing time) to the time of the last quantifiable concentration (t_{last}).
C_{max}	Maximum observed concentration.
t_{max}	The time to reach the C_{max} in a dosing interval.
$t_{1/2}$	The terminal half-life.
t_{lag}	The time prior to the first concentration at or above LOQ.
CL/F	The apparent total body clearance following extravascular administration.
V_z/F	The apparent volume of distribution during the terminal phase following extravascular administration.
F_{rel}	Relative Bioavailability [%] of each Batch in relation to the Reference Batch (treatment A) will be calculated: $F_{rel} = 100 \times (AUC_{0-\infty} \text{ [Batch]} \times \text{Dose}_{\text{[Reference Batch]}}) / (AUC_{0-\infty} \text{ [Reference Batch]} \times \text{Dose}_{\text{[Batch]}})$
λ_z	Terminal first order (elimination) rate constant.

Additional PK parameters may be calculated where appropriate.

Units for PK parameter outputs will be based on concentration and dose units used in the study, unless otherwise specified. If concentration data units change within the study, PK parameters will be reported using consistent units throughout study outputs. In such cases, the Sponsor will specify relevant units for reporting before the final PK evaluation.

The parameters C_{max} and t_{max} will be obtained directly from the concentration-time profiles. If C_{max} occurs at more than one timepoint, t_{max} will be assigned to the first occurrence of C_{max} .

The following PK parameters will be calculated for diagnostic purposes and listed, but will not be summarized:

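### Could an all-BLQ period or a profile cut short before its peak corrupt the primary Cmax comparison?

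*SAP*

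**What the plan says.** Five rules in the SAP bear on this point.

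- **Membership (8.1).** A participant enters the PK analysis set after at least one active dose, if they "provide at least one measurable postdose concentration. A measurement below lower limit of quantification is considered a valid measurement". Membership is per participant, not per period, and "All PK analyses will be based on the PK Analysis Set".
- **BLQ values (16.1.4).** "Values BLQ will be taken as zero for summary statistics of PK concentration data, PK parameter estimation (e.g., AUC) and for graphical presentations".
- **Early withdrawal (16.1.4).** "A participant who withdraws prior to the last planned observation will be included in the analyses up to the time of discontinuation", on the condition, stated in the same sentence, that the participant still belongs to the PK analysis set. SAP 9.4 says much the same and assumes that missing data are missing completely at random.
- **Cmax (16.1.5.1).** It is the "Maximum observed concentration" and, with tmax, "will be obtained directly from the concentration-time profiles". No minimum number of samples or minimum sampling time is given.
- **Primary model (16.1.3).** A linear mixed model "will be applied to log-transformed primary endpoints" Cmax and AUC0-∞. Differences from batch A "on the log scale for each comparison will be estimated for the parameters together with their 90% CIs".

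Protocol 9.1 calls the analysis descriptive, without hypothesis tests.

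**The concern.** The second half of the membership rule appears to cancel the first: a participant with nothing but BLQ values after dosing would qualify. With BLQ set to zero, that period's Cmax is 0, and a log-scale model cannot use it. The SAP does not say what happens then.

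The second worry is less visible. A participant who stops sampling while concentrations are still rising has a largest observed value, and by definition that value is Cmax. It is a positive number, so the model accepts it. The numerical acceptance criteria in SAP 16.1.5.1 (extrapolated share, adjusted R², span ratio) all concern the terminal slope; none tests whether the peak was reached.

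Cmax is a primary endpoint. One badly low value would shift a batch ratio and, through the pooled residual variance, widen the interval for every comparison.

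**Working it through.** The visible documents give no sample-size calculation, CV or acceptance range (the protocol text after 9.1 is blacked out), so there is no stated figure to reproduce. The check traces the rules first, then sizes the effect.

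**1. A period with only BLQ values**

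- Cmax = 0 and log(0) is undefined. The record has no response value, so it cannot enter the fit.
- AUC0-∞ needs a terminal slope from at least 3 time points, and BLQ values after the last quantifiable point are not used (SAP 16.1.5.1). With no quantifiable point there is no slope, so AUC0-∞ is missing, not zero.
- The participant's other periods remain in the mixed model.

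The outcome is the same as under a rule that sets the period to missing. Individual concentrations and parameters are listed in any case (SAP 16.1.6.1).

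**2. A profile that stops before its peak**

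- AUC0-∞: the concentration at tmax is kept out of the slope regression. A profile still rising at its last sample has no later points, so AUC0-∞ is again missing.
- Cmax: the last rising value qualifies on a literal reading. Only this case can reach the primary model.
- If sampling stops after the peak, the observed Cmax is correct.

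**3. What one truncated Cmax would do**

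Inputs: n = 7 × 4 = 28 at most (Protocol 6.3.1). The fraction f of the true peak that was observed, n = 24 and the within-participant CV are assumptions; the documents give none.

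In a complete balanced crossover each batch mean on the log scale averages n values, so one offset of ln f moves that mean by ln f / n. The ratio to A is multiplied by f^(1/n) if a test batch is affected. If A is affected, all three ratios are multiplied by f^(−1/n).

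| f | Test batch, n = 28 | Reference, n = 28 | Test batch, n = 24 |
|---|---|---|---|
| 0.50 | −2.4% | +2.5% | −2.8% |
| 0.20 | −5.6% | +5.9% | −6.5% |
| 0.05 | −10.1% | +11.3% | −11.7% |

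These figures apply when the stop is in Period 4, since all four values are then present. A stop in Period 1 leaves the participant with a single value, which their own effect absorbs, so there is essentially no shift. For Periods 2 and 3 at f = 0.20 the shift is at most 5.9%, in either direction.

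**4. Interval width (assumed CV 30%, n = 28, participant fitted as fixed)**

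- σ² = ln(1 + 0.30²) = 0.0862; residual df = 112 − 28 − 3 − 3 = 78.
- Complete data: exp(1.665 × √(2 × 0.0862 / 28)) = 1.14, a half-width of about 14%.
- f = 0.20: added residual sum of squares = (ln 0.20)² × (1 − 34/112) = 2.590 × 0.696 = 1.80. Residual SD rises by √(1 + 1.80 / (78 × 0.0862)) = 1.13, and the half-width becomes about 16%.
- f = 0.05: the same steps give a factor of 1.39 and a half-width of about 20%.

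**5. With the value left out**

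In 2,000 simulated trials at CV 30%, omitting the one affected value returned the ratio to 1.00, with a half-width factor of 1.140 against 1.138 for complete data. Excluding such a value at review therefore costs almost nothing.

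**6. What already stands in the way**

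- SAP 16.1.5.1 has parameters calculated only where suitable, which allows a Cmax to be withheld from an unevaluable profile.
- SAP 16.1.4 requires affected concentrations and PK parameters to be left out of further statistical evaluation after important deviations likely to alter the profile. The list in 10.2.1 covers deviations and events, is open-ended, and names adverse events, vomiting and dosing errors: plausible reasons for stopping soon after a dose.
- SAP 6 places a data review meeting before database lock. Protocol 8.4.1 asks for an eCRF comment on departures from the sampling windows and allows them to be raised there.
- Protocol 7.2: if consent is revoked, samples are destroyed, so any not yet assayed yield no concentration.
- Participants are resident from Day −1 to Day 8 and are sampled at 0.25, 0.5, 1, 1.5, 2, 2.5 and 3 hours (Protocol 1.1 and 1.3). Dosing is supervised, with a mouth check (Protocol 6.4).

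**The case for a change.** The strongest case for a change is that every safeguard is discretionary. The list in SAP 10.2.1 names neither early withdrawal nor an all-BLQ profile, and the proviso in 16.1.5.1 has no criterion attached. SAP 16.1.4 also keeps concentrations that merely look implausible. The study is open-label, so a decision to drop a primary value would be made with the batch known. The remedy would be a few lines, and section 5 of the working shows that it loses almost no precision.

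Part of this stands. The wording in 8.1 is loose, no period-level rule for Cmax is written down, and a truncated value that survived review would act directly on a primary estimate.

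The rest carries less weight. The rule on implausible values concerns concentrations. In a truncated profile the concentrations are right; the question is whether their maximum is a peak, and that can be settled from recorded sampling times without reference to batch. Exclusions have to be listed, flagged and explained (SAP 10.2.2 and 16.1.4), so a reader can see and reverse them. For the BLQ and AUC0-∞ parts, a written rule would leave the result unchanged.

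**Conclusion.** No change is needed. For an all-BLQ period, and for AUC0-∞ in a profile that stops before its peak, the plan already arrives at a missing value, so a new rule gains nothing. For a truncated Cmax the SAP lacks a detail that the pharmacokineticist and the data review can be expected to supply, using exclusion powers the plan already contains.

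If one such value nevertheless stayed in, the shift with 28 participants would be about −5.6% for a test batch, or +5.9% for all three ratios if the reference were affected, at 20% of the true peak. It would be about −2.4% or +2.5% at 50%, and close to nil for a stop in Period 1. These sizes rest on assumed fractions. The visible documents give no tmax, so they cannot show whether fractions as low as 5% or 20% are realistic; the interval widths also rest on an assumed CV of 30%. The judgement that the event is rare rests on residence, supervised dosing and dense early sampling, not on a stated rate. Protocol 9.3, which defines the analysis sets, is blacked out and could not be compared with SAP 8.1.
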